### 7.1.1 Sensitivity Analyses

#### Multiple Imputation with Fully Conditional Specification (FCS) Method

Multiple imputation, using the FCS method will be used as a sensitivity analysis for the analysis of the primary efficacy endpoint. This analysis is described in detail in **Section 7.5.4**.

### 7.1.2 Tipping Point Analyses

As the primary analysis (mixed effects model for repeated measures [MMRM]) relies on the missing at random (MAR) assumption, to evaluate the robustness of the primary analysis approach, a sensitivity analysis using the tipping-point approach will be conducted. This analysis is described in **Section 7.5.4**.

## 7.2 Subject Disposition

Disposition for all subjects will be tabulated and listed. The tabulation will include the number of subjects consented, screened, randomized, treated, randomized but not treated, the number of subjects completing the placebo-controlled period, the number of subjects who complete the extension period, the number of subjects who complete the follow-up period, and the number of subjects who discontinue the study early will also be presented. For subjects who discontinue, the reason for discontinuation will also be included. The number and percentage of randomized subjects included in the ITT, PP, Extension, Safety, and PK Analysis Sets will also be tabulated.

Randomization stratification factors and treatment assignment will be listed together. If there are any subjects who took study treatment other than what was randomized during the study, both the treatment assigned at randomization and actual treatment(s) received during the double-blind treatment period will be listed. The duration of actual treatment will also be listed.

A listing of reasons why subjects were not randomized will be provided for all subjects who were not randomized. The reason for exclusion of a subject from the PP, Safety, and PK Analysis Sets will be listed for all randomized subjects; Coronavirus disease 2019 related reasons for exclusion from the PP Analysis Set may be considered. In addition, randomized subjects who violate inclusion/exclusion criteria and the important protocol deviations will be listed.

## 7.3 Deviations

All protocol deviations will be identified and discussed with the Sponsor during the BDRM prior to final database lock. Important protocol deviations for exclusion from the PP Analysis Set will be determined and appropriately categorized in this meeting. These are defined as potential protocol deviations that may significantly affect the reliability of efficacy study data.

All important protocol deviations will be summarized by treatment group and overall subjects for the ITT Analysis Set. All protocol deviations will also be listed.

## 7.4 Demographic and Baseline Characteristics

### 7.4.1 Demography and Physical Characteristics

Demographics and baseline characteristics variables which are listed in **Section 6.1** will be summarized overall and by treatment and all data will be provided in listings. Continuous baseline demographic and disease characteristics (such as age, height, weight, BMI, AN count, total abscess count, total inflammatory nodule count, draining fistula count, and HS pain NRS), will be summarized descriptively using number of subjects, mean, median, standard deviation, minimum, maximum, first quartile, and third quartile. For categorical baseline disease characteristics and demographic parameters (such as country, reproductive status, sex, ethnicity, race, Hurley Stage, smoking history, Fitzpatrick skin type, HS-PtGA, DLQI, HiSQoL,

HS-PGA, IHS4, PGI-B and PGI-S), the number and frequencies and percentages of subjects will be provided along with descriptive statistics treating them as a continuous variable.

#### 7.4.2 Medical and Surgical History

Medical and surgical history will be summarized for the Safety Analysis Set and listed for all randomized subjects.

#### 7.4.3 Prior, Concomitant, and Rescue Medications/Treatments

Refer to **Appendix 1** for definitions of prior and concomitant treatments. Prior, concomitant, and rescue medications/treatments will be summarized by ATC class, preferred name and actual treatment received for the Safety Analysis Set. In summary tables, subjects will only be reported once for the medication or for the class of drugs he/she has taken. Prior, concomitant and rescue medications will be displayed in separate listings.

### 7.5 Efficacy Analyses

The ITT Analysis Set will be used as the primary analysis set for all efficacy analyses in the placebo-controlled period. The Extension Analysis Set will be used as the main analysis set for all efficacy analyses in the extension period.

Per protocol analyses will be performed on the primary as well as the following secondary endpoints:

- Percent change from baseline in AN count at each visit
- Proportion of subjects achieving HiSCR50 at each visit
- Change from baseline in HS Pain NRS at each visit
- Percent change from baseline in HS Pain NRS at each visit

All statistical tests will be performed at the 10% level of significance unless otherwise stated. All confidence intervals will be reported as 2-sided 90% confidence intervals unless otherwise stated. Descriptive statistics will be provided for the continuous variables as number of subjects, mean, standard deviation, standard error of the mean, first and third quartiles, minimum, and maximum. Descriptive summaries of continuous variables will be shown for baseline, change from baseline to endpoint, and percent change from baseline to endpoint. All data will be listed in data listings.

#### 7.5.1 Primary Efficacy Estimand

The primary estimand, comprising five components, is as follows:

- a) The target population is subjects in the United States and Europe diagnosed for at least 6 months with HS, having lesions at Hurley Stage II or III.
- b) The primary variable is the change from baseline in AN count of an individual subject at Week 16.
- c) To handle intercurrent events such as use of rescue medications, a hypothetical strategy for estimand (**ICH E9, 2019**) will be used such that data collected following receipt of rescue medication (if any) will be considered missing in the analysis. Missing values will be imputed as described in **Section 7.5.4**. The hypothetical scenario envisaged under this estimand is what value the primary variable would have taken if the subject had not taken rescue treatment.

- d) The population-level summary measure for the primary endpoint is mean change from baseline in AN count at Week 16. The estimator for between-group comparison of the primary endpoint will be the difference in the primary endpoint between imidolimab and placebo at Week 16.
- e) The treatment conditions of interest, two imidolimab treatment regimens and one placebo regimen:
  1. Imsidolimab 400 mg injection on Day 1, followed by 200 mg on Days 29, 57, and 85;
  2. Imsidolimab 200 mg injection on Day 1, followed by 100 mg on Day 29, 57, and 85;
  3. Placebo on Days 1, 29, 57, and 85

A linear mixed model will be used for the repeated measures (MMRM) with treatment, visit, treatment by visit interaction, and Hurley Stage at baseline as a categorical covariate and baseline AN count as a continuous covariate. An unstructured correlation (UN) matrix will be used to model correlation within a patient; if convergence is an issue, a Toeplitz structure may be considered. If convergence issue persists, elimination of post-baseline visits other than Week 16 may be considered. Subjects with missing data at Week 16 due to early discontinuation will be included in the model.

The least squares (LS) mean and the standard error of this mean with the corresponding two-sided 90% confidence interval will be provided for each treatment based on the model. The LS mean difference between treatments (imidolimab - placebo), as well as the corresponding two-sided 90% confidence interval will be provided based on the model. Summary statistics and the results of statistical testing in AN count at Week 16 will be tabulated. The LS mean change from baseline in AN count will be plotted against post-baseline visits for each treatment group. The LS mean difference and corresponding confidence intervals will also be plotted.

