#### 9.4.5 ANALYSIS OF THE PRIMARY EFFICACY ENDPOINT

The primary efficacy endpoint is the change from Baseline in AN count at Week 16.

The primary estimand, comprising four components, is defined as follows:

- a) The target population consists of subjects with hidradenitis suppurativa who are eligible to be included in the clinical trial based on the inclusion/exclusion criteria in the protocol. The ITT analysis set will include all randomized subjects. For the analysis, treatment will be assigned based upon the treatment arm to which subjects are randomized regardless of which treatment they receive.
- b) The primary variable is the change from baseline in AN count of an individual subject at Week 16.
- c) To handle intercurrent events such as use of rescue medications, the hypothetical strategy for estimand will be used. Data collected following receipt of rescue medication (if any) will be considered missing in the analysis.
- d) The population-level summary measures will be the population mean differences in the primary variable between each dose of imsidolimab and placebo at Week 16.

A general linear mixed effects model for repeated measures (MMRM) analysis will be used to estimate the least squares means (LSM) and associated standard errors for the change from Baseline in AN count to Week 16. The model will include change from Baseline in AN count at Week 16 as the dependent variable, fixed effects for treatment arm, categorical time point, and the treatment by time point interaction, and the Baseline AN count and stratification factor (ie, Hurley Stage at baseline (Stage II or III)) as covariates. An unstructured covariance structure will be used. The difference between LSMs (imsidolimab – placebo) at Week 16 will be presented along with the associated 90% CI and p-value. The ITT analysis set will be used for the primary efficacy analysis.

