### 3.3 Hypothesis Testing

The primary analysis for this study is to compare the mean change from baseline in AN count for imsidolimab vs. placebo at Week 16 of the double-blind treatment period, at a two-sided alpha = 0.10 level. The following hypothesis test will be done separately for each imsidolimab dose arm.

$$H_0: \mu_{\text{imsidolimab}} - \mu_{\text{placebo}} = 0 \text{ vs. } H_A: \mu_{\text{imsidolimab}} - \mu_{\text{placebo}} \neq 0$$

Treatment comparisons may be performed for the secondary or exploratory endpoints and will be considered exploratory in nature. Two-sided p-values and 90% confidence intervals will be produced.

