## APPENDIX 2 SAS CODE FOR STATISTICAL ANALYSES

This section will be completed after examining the existing data and prior to the final signoff of this SAP.

Test	Template SAS Code for Modeling (SAS Version 9.4)
Linear Repeated Measures Analysis of Covariance for the primary endpoint	<pre> PROC MIXED METHOD=REML;   CLASS SUBJECT TRT VISIT BASEHSSTAGE;   MODEL Y = BASE TRT VISIT TRT VISIT/ DDFM=KR SOLUTION   OUTP=OUT;   REPEATED VISIT / TYPE = UN SUBJECT = SUBJECT;   LSMEANS TRT VISIT / PDIFF CL ALPHA=0.1;   ODS OUTPUT LSMEANS=MEANS;   ODS OUTPUT DIFFS=DIFF;   RUN; </pre> 
Where TRT is treatment, VISIT is the study visit number, BASEHSSTAGE is the baseline Hurley Stage, and BASE is the baseline of outcome variable.

General Estimating Equation Repeated Measures with Generalized Logit Transformation	<pre> PROC GENMOD;   CLASS SUBJECT TRT VISIT BASEHSSTAGE;   MODEL Y= BASE TRT VISIT TRT*VISIT / LINK=LOGIT DIST=NEGBIN;   REPEATED SUBJECT=SUBJECT / TYPE=UN;   LSMEANS TRT VISIT / DIFF CL ALPHA=0.1;   ODS OUTPUT LSMEANDIFFS = LSDIFS ESTIMATES=EST   LSMEANS=LSMEANS PARAMETERESTIMATES=PE; </pre> 
Where TRT is treatment, VISIT is the study visit number, BASEHSSTAGE is the baseline Hurley Stage, and BASE is the baseline of outcome variable.

General Estimating Equation Repeated Measures for secondary and exploratory endpoints	<pre> PROC GENMOD;   CLASS SUBJECT TRT VISIT;   MODEL Y = TRT VISIT TRT*VISIT/ DIST=BIN LINK=LOGIT;   REPEATED SUBJECT = SUBJECT /TYPE=UN;   RUN; </pre> 
Where TRT is treatment and VISIT is the study visit number.

Test	Template SAS Code for Modeling (SAS Version 9.4)
Impute Intermittent Missing using the Monte Carlo Markov Chain (MCMC) approach	<pre> PROC MI DATA=data_in SEED=2330710 NIMPUTE=100 OUT=LESION_MONO;   BY BASEHSSTAGE TRT; /*Assuming different treatment, baseline Hurley Stage has different distribution*/   MCMC CHAIN=MULTIPLE IMPUTE=MONOTONE; /*Only impute intermittent missing values*/   VAR AGE BASE AN1 – AN5; /*Impute AN count from Week 4 to Week 16, with age and baseline as covariates*/   RUN; </pre>
Multiple Imputation with FCS Method	<pre> PROC MI MIN=0 ROUND=1;   CLASS BASEHSSTAGE TRT SEX;   FCS REGPMM(AN2 = AN1 AGE SEX TRT BASE BASEHSSTAGE );   FCS REGPMM(AN3 = AN1 AN2 AGE SEX TRT BASE BASEHSSTAGE );   FCS REGPMM(AN4 = AN1-AN3 AGE SEX TRT BASE BASEHSSTAGE );   FCS REGPMM(AN5 = AN1 AN4 AGE SEX TRT BASE BASEHSSTAGE );   VAR AN1 – AN5 AGE SEX TRT BASE BASEHSSTAGE;   RUN; </pre>

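### The primary MMRM fits one baseline AN slope for all visits; a baseline-by-visit term would protect Week 16 precision at almost no cost

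*SAP*

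**What the plan says.** SAP 7.5.1 lists the model terms as treatment, visit, "treatment by visit interaction, and Hurley Stage at baseline as a categorical covariate and baseline AN count as a continuous covariate". Protocol 9.4.5 describes the same model: "fixed effects for treatment arm, categorical time point, and the treatment by time point interaction, and the Baseline AN count and stratification factor". The template in SAP Appendix 2 also carries the baseline once: "MODEL Y = BASE TRT VISIT TRT VISIT/ DDFM=KR SOLUTION". (The second treatment and visit pair there is read as the interaction, its operator probably lost in text extraction. Baseline Hurley Stage is missing from the MODEL line, which is a separate matter.)

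The covariance is left free: "An unstructured correlation (UN) matrix will be used to model correlation within a patient; if convergence is an issue, a Toeplitz structure may be considered". The last fallback is "If convergence issue persists, elimination of post-baseline visits other than Week 16 may be considered".

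The sensitivity analyses in SAP 7.5.4 add race, smoking, age and skin type to the model, but not a baseline-by-visit term.

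**The concern.** The outcome is change from baseline. If the AN count at visit t has slope b_t on the baseline count, the change has slope b_t − 1. When later counts correlate less with baseline than earlier ones, b_t falls and the slope of the change steepens toward Week 16. The planned model must fit one compromise value. At Week 16, part of the baseline-explained variation then stays in the residual, and the primary contrast is less precise than the same data allow.

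The plan also treats the baseline differently from place to place. The FCS and tipping-point imputations in SAP 7.5.4 regress each visit separately on baseline, which allows visit-specific slopes. The MMRM then applied to the imputed data forces one slope. The last convergence fallback keeps Week 16 alone and so uses a Week 16 slope. How the primary result is adjusted for baseline would therefore depend on whether the model converged.

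**Working it through.** **The plan's own figure.** Protocol 9.2 gives 36 evaluable subjects per arm, a difference of 4.9 lesions, SD 8.2 and two-sided alpha 0.10. The noncentrality is 4.9 / (8.2 × √(2/36)) = 2.54 on 70 df, and noncentral-t power is 80.7%. The stated 80% reproduces, as do all 24 entries of protocol Table 6 to within 1 point. That calculation is an unadjusted t-test with no baseline covariate.

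**Formulas (complete data).** Let b be the vector of slopes of the four post-baseline counts on baseline, and C their covariance given baseline.

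- Common slope under GLS: b̄ = 1′C⁻¹b / 1′C⁻¹1. Re-estimating the unstructured covariance under the common-slope model leaves b̄ unchanged.
- Week 16 residual variance with visit-specific slopes: C₄₄.
- Week 16 residual variance with a common slope: C₄₄ + (b₄ − b̄)² Var(baseline).
- Information loss: 1 − C₄₄ / (common-slope variance).

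The documents give no inter-visit correlations, visit-specific variances or baseline SD. Every structure below is therefore an assumption.

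**Equal-variance AR(1), unit variance, 4-week correlation ρ.** Here b₄ = ρ⁴, b̄ = ρ / (1 + 3(1 − ρ)²) and C₄₄ = 1 − ρ⁸. At ρ = 0.785, near the worst case:

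- b₄ = 0.380 and b̄ = 0.785 / 1.139 = 0.689.
- C₄₄ = 0.856.
- Common-slope variance = 0.856 + 0.310² = 0.952.
- Ratio 0.952 / 0.856 = 1.112, so variance is 11.2% higher and the information loss is 1 − 1/1.112 = 10.1%.

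| ρ | Week 4 weight in slope | Common slope of change | Week 16 slope of change | Variance inflation | Information loss |
|---|---|---|---|---|---|
| 0.5 | 43% | −0.71 | −0.94 | 5.0% | 4.8% |
| 0.6 | 51% | −0.59 | −0.87 | 7.7% | 7.2% |
| 0.7 | 62% | −0.45 | −0.76 | 10.3% | 9.3% |
| 0.785 | 73% | −0.31 | −0.62 | 11.2% | 10.1% |
| 0.9 | 88% | −0.13 | −0.34 | 8.3% | 7.7% |
| 0.95 | 95% | −0.06 | −0.19 | 4.9% | 4.7% |

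**Other structures (information loss).**

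- Compound symmetry: each visit carries 25% of the weight, and the loss is 0.
- AR(1) plus measurement error at 20 to 40% of variance: about 1 to 4%.
- Random intercept, AR(1) and measurement error together: 0.4 to 1.9%.
- Random intercept plus AR(1), no error: 3.7 to 7.1%.
- Correlation falling linearly with lag: 1.3 to 6.8%, and 13.6% for a steep fall from 0.80 to 0.35.
- AR(1) with SD falling to 0.8 or 0.6 of baseline: 7.5 to 24.5%.
- AR(1) with SD rising to 1.3 or 1.4 of baseline: 0.2 to 6.1%.

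**Simulation check.** With three arms of 36 and 3,000 runs, the loss was about 6%, 12% and 5% at ρ = 0.6, 0.78 and 0.9, in line with the formula given Monte Carlo error. With no true effect, the mean estimated difference was about 0.

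**Effect on power at the AR(1) worst case, 36 per arm.** If 8.2 is the SD of raw change, whose variance here is 2(1 − ρ⁴) = 1.24:

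- Common slope: SD 8.2 × √(0.952/1.24) = 7.18, power 88.9%.
- Visit-specific slopes: SD 8.2 × √(0.856/1.24) = 6.81, power 91.6%.

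If 8.2 is already the residual SD with visit-specific slopes, the common slope raises it to 8.2 × √1.112 = 8.65 and power is 76.9% rather than 80.7%. In subjects, the loss is 36 × 0.856/0.952 = 32.4 per arm instead of 36.

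**The case against.** A single main-effect baseline covariate is a legitimate, prespecified choice, and it is consistent across protocol, SAP and code. The objections to making much of it are good ones, and most of them limit the size.

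- A reader might infer that the slope is set mainly by early visits. The documents do not show this. It needs decaying correlation with roughly stable variance. Under compound symmetry the visits weigh equally, and under AR(1) with SD falling to 0.6 of baseline, Week 16 itself carries 41 to 50% of the weight.
- A reader might take about 11% of the information as the ceiling. The 11.2% is variance inflation under one assumed structure; the matching information loss is 10.1%. Nor is it a bound, since other structures give from 0 to about 25%.
- Pure AR(1) has no counting error. Protocol 4.2 describes HS efficacy assessments as highly subjective, and protocol 8.1 asks for the same assessor to limit variability. Some measurement error is therefore expected, which points to the lower figures.
- A reader might infer a biased or underpowered primary test. With complete data, randomization keeps the Week 16 contrast unbiased. In every structure tried, the common-slope variance stayed below that of the unadjusted change used for sizing (ratio 0.32 to 0.998).
- A reader might extend the same loss to every endpoint analyzed with a similar MMRM. Only change in AN count was modelled. Percent change relates to baseline differently, and nothing was computed for it or for pain NRS.

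What stands is that the term is absent everywhere, that it can only matter in one direction to any real degree, and that its cost is trivial. Under compound symmetry the variance ratio of common to visit-specific slopes was 0.995, so adding the term cost about half a percent. The calculations above assume complete data. A small simulation (300 trials per scenario, about 20 to 25% missing at Week 16 depending on the preceding count) still showed a larger standard error with the common slope and no meaningful bias.

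**Conclusion.** The point holds as an inexpensive gain in precision. The primary model imposes one baseline AN slope on four visits when only one of them is primary. If correlation with baseline decays, the Week 16 contrast is under-adjusted.

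The information loss is 0 under compound symmetry, about 1 to 4% with measurement error, and about 7 to 10% under equal-variance AR(1) with a 4-week correlation of 0.6 to 0.9. It is possibly more if variance falls over time. All of these rest on assumed correlation structures, because the documents supply none.

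The planned 80% power is not undercut if 8.2 is the SD of raw change, which is the natural reading of a sample size built on an unadjusted t-test of change. Only if 8.2 were already the visit-specific residual SD would power fall below target, to about 77% in the AR(1) worst case.

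**What to change.** Add baseline AN count by visit to the primary MMRM, in the text of SAP 7.5.1 and as BASE*VISIT in the Appendix 2 MODEL statement. Record it in SAP section 8 as a change from protocol 9.4.5. Keep the term under the Toeplitz fallback and in the MMRMs fitted after imputation, so that the imputation and analysis models agree on how baseline enters.

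For consistency, use the matching baseline-by-visit term in the other change-from-baseline MMRMs; the gain there has not been quantified.

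The cost is three fixed-effect parameters among about 120 subjects, with no new data and essentially no loss if the slopes are equal. The change should be made before the primary analysis data snapshot, by which SAP section 4 commits to finalizing the plan, so that the choice is not made after unblinding.

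### If ever used, the last convergence fallback in SAP 7.5.1 would leave a Week-16-only ANCOVA on completers and contradict the sentence that follows it

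*SAP*

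**What the plan says.** SAP 7.5.1 analyses change from baseline in AN count with a repeated-measures mixed model. Its terms are treatment, visit, their interaction, baseline Hurley Stage and baseline AN count. The covariance starts as unstructured, and two fallbacks follow: "if convergence is an issue, a Toeplitz structure may be considered", and then, if the model still does not converge, "elimination of post-baseline visits other than Week 16 may be considered". The next sentence reads: "Subjects with missing data at Week 16 due to early discontinuation will be included in the model".

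Three other places bear on this:

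- Component (c) of the estimand in the same section treats counts after rescue as missing and adds "Missing values will be imputed as described in" Section 7.5.4.
- SAP 7.1.1 gives imputation a different status: "Multiple imputation, using the FCS method will be used as a sensitivity analysis for the analysis of the primary efficacy endpoint". SAP 7.1.2 states the basis of the primary model: "As the primary analysis (mixed effects model for repeated measures [MMRM]) relies on the missing at random (MAR) assumption".
- The Appendix 2 code for the primary endpoint puts baseline on the right-hand side of the model and uses the post-baseline visits as the repeated responses: "REPEATED VISIT / TYPE = UN SUBJECT = SUBJECT".

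Protocol 9.4.5 specifies an unstructured covariance on the ITT set and gives no fallback. SAP Section 8, which lists changes from the protocol, does not mention one.

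**The concern.** With Weeks 4, 8 and 12 removed there is no repeated measure left. The model becomes a cross-sectional ANCOVA at Week 16, and a subject without a usable Week 16 count has no response to enter. The inclusion sentence is unconditional, so the two adjacent sentences cannot both be followed once the fallback is used.

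The assumption changes as well. The all-visits likelihood is valid when missingness depends on observed earlier counts. The Week-16-only ANCOVA needs missingness to depend only on treatment and baseline covariates. The hypothetical strategy for rescue asks what the count would have been without rescue, and the fallback deletes the pre-rescue counts that inform the answer. SAP 7.5.1 also promises a plot of least-squares means across post-baseline visits, which a one-visit model cannot supply.

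At stake is a possibly biased primary estimate that departs from ITT, chosen under wording that leaves the step to discretion.

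**Working it through.** **1. The plan's own figure.** Inputs from Protocol 9.2 and SAP 3.5: 120 randomized 1:1:1 (40 per arm), 10% dropout before Week 16, difference 4.9, SD 8.2, two-sided alpha 0.10.

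- Evaluable: 120 × 0.90 = 108, or 36 per arm.
- Standard error of the difference: 8.2 × √(2/36) = 1.93. Noncentrality: 4.9 / 1.93 = 2.53.
- Power from the noncentral t with 70 degrees of freedom: 80.7%. The stated 80% reproduces, and it already rests on 36 completers per arm.

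**2. Who contributes.** Suppose 12 subjects (10%) lack Week 16 but have the earlier visits.

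- All visits kept: 120 subjects, 120 × 4 − 12 = 468 response rows.
- Week 16 only: 108 subjects, 108 response rows.

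Protocol 9.4.4 also sets efficacy data to missing on and after rescue. The documents give no rescue rate. As an assumption, if 0%, 5% or 10% of the 108 were rescued before their Week 16 assessment, the Week-16-only model would hold 108, about 103 (108 × 0.95 = 102.6) or about 97 (108 × 0.90 = 97.2) subjects.

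Even the all-visits model omits a subject with no post-baseline count, so the inclusion sentence is slightly too broad in any case.

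**3. How likely the trigger is.** Four visits give 4 × 5 / 2 = 10 unstructured covariance parameters for about 120 subjects, and Toeplitz is tried next. In 4,500 simulated two-arm trials (80 subjects, AR(1) correlation 0.7, SD 8.2, 11% to 25% missing at Week 16 per arm), an unstructured maximum-likelihood fit converged every time. That fit used EM rather than the planned SAS REML, so it is indicative only.

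**4. Size of the bias.** All dropout mechanisms below are assumptions, not taken from the documents.

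First scenario: 1,500 trials, 40 per arm, AR(1) correlation 0.7, SD 8.2, logistic dropout on the last change (12% placebo, 8% active), true difference −4.9. Completers at Week 16 gave −4.75, and sequential regression using all visits gave −4.96. The completer bias is 4.90 − 4.75 = 0.15 lesions. That is 0.15 / 4.9 = 3% of the effect and 0.15 / 1.93 = 0.08 standard errors, toward the null. Monte Carlo error is about 1.9 / √1500 = 0.05.

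Second set: same arm size, SD and true difference, with dropout depending on the previous value at 1.5 log-odds per SD. Neither estimate adjusts for baseline covariates. Each cell shows all visits / Week 16 only.

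| Correlation | Same mechanism, about 8% dropout | Same mechanism, about 20% | Opposite mechanisms, about 13% |
|---|---|---|---|
| 0.5 | −4.94 / −4.80 | −4.88 / −4.60 | −4.87 / −3.99 |
| 0.7 | −4.92 / −4.71 | −4.91 / −4.48 | −4.85 / −3.39 |
| 0.9 | −4.90 / −4.58 | −4.91 / −4.33 | −4.91 / −2.73 |

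In the last column, worsening placebo subjects and improving active subjects leave.

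**The case against.** The strongest reply is that this is a remote, optional step. It needs two convergence failures, and even then it is only to be considered; SAP Section 1 requires any departure to be justified statistically. Toeplitz, the first fallback, keeps every visit. The multiple imputation and tipping-point analyses in SAP 7.5.4 use the earlier visits and are planned whatever happens, so an estimate retaining these subjects would sit beside any Week-16-only result. All of this stands and keeps the point small.

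Two further replies stand only in part. The imputation sentence in component (c) would, if applied to the primary analysis, bring the missing subjects back in. But SAP 7.1.1 and 7.5.4 make imputation a sensitivity analysis and 7.1.2 rests the primary model on missing at random, so that sentence also needs reconciling. The fallback could also be read as dropping only some earlier visits. The plain wording removes all of them, and the SAP should say which is meant.

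Several stronger readings are tempting but unsupported:

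- **That the primary analysis is a complete-case analysis.** It becomes one only if the last fallback is used.
- **That planned power is lost.** The 80% is already computed on completers.
- **That response-dependent dropout is the documented pattern.** Protocol 6.6 allows rescue from Week 8 for an intolerably painful lesion, and Protocol 7.2 lists disease progression as a reason to stop. These make it plausible, but nothing ties missingness to earlier AN counts.
- **That a large bias should be expected.** The large values above need opposite dropout mechanisms in the two arms, which the documents do not suggest.

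**Conclusion.** The inconsistency is real, rests on the text alone, and bites only if the last fallback is invoked. The primary analysis would then be an ANCOVA on about 108 of 120 subjects, less anyone rescued before Week 16. It would contradict the inclusion sentence and discard the counts behind the missing-at-random assumption.

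The trigger is unlikely and planned power is unaffected. The bias is probably small: 0.15 lesions in the first scenario, and 0.10 to 0.32 (4.90 minus 4.80 to 4.58) under a common mechanism at about 8% dropout. It could reach 0.91 to 2.17 (4.90 minus 3.99 to 2.73) if mechanisms were opposite between arms. These sizes depend on the assumed dropout models. If missingness depends only on treatment and baseline covariates, the Week-16-only ANCOVA is valid. This is a low-severity correction that is worth making because it costs so little.

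**What to change.** In SAP 7.5.1, replace the last step with a prespecified order that keeps all four visits and takes the first structure that converges:

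1. unstructured (10 parameters);
2. heterogeneous Toeplitz (4 variances + 3 correlations = 7);
3. heterogeneous AR(1) (4 + 1 = 5);
4. compound symmetry (2), with sandwich standard errors.

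Alternatively, keep a Week-16-only ANCOVA as the last resort, but require the Section 7.5.4 multiple imputation from earlier visits before it is fitted. In either case, state whether the imputation sentence in component (c) applies to the primary analysis, limit the inclusion sentence to subjects with at least one usable post-baseline count, and list the fallback in SAP Section 8, since Protocol 9.4.5 names only the unstructured form.

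The cost is a few sentences of SAP text and no new data. The downside is that a simpler covariance may be misspecified. The sandwich protects the standard error but does not remove bias in the point estimate when data are missing at random, so the richer structures come first.
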